#### **4.0 Inclusion/Exclusion Criteria**

There will be no restriction on gender (except pregnant women), race, age (except less than 30 or greater than 80 years old) or disease etiology for subject selection or exclusion except as stated below.

##### Inclusion Criteria:

1. Age 30 to 80 years;
2. Systolic blood pressures between 110 to 150 mmHg and/or diastolic blood pressure between 80-99 mmHg;
3. Ability to give informed consent.

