##### Exclusion Criteria:

1. Pregnancy;
2. Intolerance to study protocols;
3. Acute cardiovascular events within the previous 6 months;
4. Impaired renal function (estimated GFR < 45 ml/min/1.73m^2);
5. Current or recent treatment with systemic glucocorticoid therapy (within 1 month of enrollment);
6. Current use of anti-hypertensive medication (except calcium channel blockers and beta blockers);
7. Diabetes mellitus requiring medical therapy;
8. Morbid obesity (BMI > 45);
9. Prior adverse reaction to a thiazide or spironolactone;
10. Claustrophobia preventing the patient from having an MRI or other contraindications to MRI;
11. Impaired hepatic function (aspartate amino transaminase and/or alanine amino transaminase > 1.5x upper limit of normal range);
12. Current illicit drug use.

13. Sexually active women of childbearing potential\*\* who are unwilling to practice adequate contraception during the study (adequate contraceptive measures include stable use of oral contraceptives or other prescription pharmaceutical contraceptives for 2 or more menstrual cycles prior to screening; intrauterine device [IUD]; bilateral tubal ligation; vasectomy; condom plus contraceptive sponge, foam, or jelly, or diaphragm plus contraceptive sponge, foam, or jelly).

\*\*Postmenopausal women must be amenorrheic for at least 12 months in order **not** to be considered of child bearing potential. Pregnancy testing and contraception are not required for women with documented hysterectomy or tubal ligation.

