## 5.0 Enrollment/Randomization

The study will be conducted at the Vanderbilt University Medical Center. Institutional Review Board approval and written informed consent will be obtained from all study subjects.

We propose to study a total of 200 subjects controlled for race (50% African Americans, 50% Caucasians) and gender (50% female, 50% male). Subjects will be recruited from the Outpatient Clinics at VUMC (including the General Medicine Clinic and the Hypertension Clinic), as well as by emails, flyers, and other recruitment tools. All participants will have a baseline assessment, as well as on-going monitoring, of their health status as documented in their medical record.

[figure not shown]
Subjects will be randomly assigned to one of the study arms (diet, spironolactone, chlorthalidone, or placebo). Randomization will be determined using a stratified permuted-block randomization method. Stratification will be based on gender and race.

One treating physician will be unblinded as to whether subjects are receiving spironolactone or chlorthalidone and will guide decisions regarding subjects who develop abnormal serum potassium levels.

To specifically address Aims 1, 3 and 4, we will also enroll subjects who will only complete visits through Week 0. In addition, to aid data analysis, we will also re-enroll subjects who will complete a follow-up visit consisting of a blood draw.

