## 6.0 Study Procedures

The design is a randomized, double-blind (except for those in the diet group), placebo-controlled study. Once the subject is determined to be eligible, we will randomly assign him/her to one of the study arms (diet, spironolactone, chlorthalidone, or placebo) as depicted in **Figure 1**. Each subject will be treated for 8 weeks. During the study, subjects will receive (1) a diet containing 6 g salt per day, (2) oral administration of spironolactone (50 mg per day), (3) oral administration of chlorthalidone (25 mg/day) or (4) oral administration of matching placebo. All medications and matching placebo will be prepared and dispensed by Vanderbilt's Investigational Drug Services (IDS). Except for the diet arm, the investigators and the study subjects will be blinded to the treatment. NaMRI, Pulse wave velocity (PWV) and a hyperinsulinemic euglycemic clamp (HEGC) study will be performed at the beginning and at the end of the study. An optional DNA blood sample may also be collected.

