**Figure 1: Study Protocol**

**Safety Precautions:** In this protocol we have the following safety precautions: (1) Anti-hypertensive/diuretic medications (like the ones used in this study) may lower blood pressure excessively and/or alter serum electrolyte levels. Accordingly, we will monitor blood pressure and electrolyte levels throughout the study. Subjects who develop electrolyte imbalance will receive an electrolyte supplement or be asked to slightly change their diet. (2) Since the use of diuretics during pregnancy introduces unnecessary risk, female subjects will have a urine pregnancy test at each study visit before any research procedures are performed. (3) Since the presence of any metal introduces unnecessary risk, a screening X-ray exam will be performed to confirm the absence of any metal in subjects where that is a possibility.

**Permanent stopping criteria:** A patient will be terminated from the study for any of the following reasons:

- Persistent hyperkalemia ( $K > 5.5$  mmol/L) occurs;
- Any allergies to the drugs develop;
- Women who become pregnant;
- There are any adverse events or clinical events that the PI judges increases the risk to the patient;
- There are any signs or symptoms of decline or deterioration of their health status.

**Screening Visit:** Within about two weeks up to the start of the Treatment Phase (which begins after the Baseline Visits) and after the subject has provided informed consent, the following information will be collected:

- Demographics
- Medical history
- Concomitant medications

Also, the following procedures and assessments will be performed:

- Vital signs (including blood pressure)
- Physical exam

- CMP (comprehensive metabolic panel) unless there is a documented CMP within 1 month of the stipulated study entry date as part of routine medical care
- Pregnancy test
- X-ray exam

**Baseline Visits (Week 0):** Subjects that qualify for the study will be randomized to one of the study arms, and will be asked to come in a fasted state on two separate days (preferably consecutive but no more than about 4 weeks apart) to the General Clinical Research Center (GCRC). On one of the visits, a hyperinsulinemic euglycemic clamp (HEGC) study will be performed. At the other visit, NaMRI and pulse wave velocity (PWV) will be performed, as well as a hand grip test. These procedures are described below.

At the Baseline Visits, the following information will be collected:

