## **8.0 Reporting of Adverse Events or Unanticipated Problems involving Risk to Participants or Others**

Safety information will be assessed by subject interview. As these results are collected, all adverse events (AE) will be identified and reported to the principle investigator within fourteen (14) days. Adverse events will be reported as described below. The principal investigator (PI) is responsible for evaluating each AE and for determining whether the AE affects the risk/benefit ratio of the study and whether modifications to the protocol and consent form are required.

Treatment will be discontinued for any subject who develops conditions during the course of the study that are felt to significantly alter the risk/benefit profile for the individual subject.

**Adverse event grading.** All adverse events will be graded as follows:

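### The and/or in inclusion criterion 2 lets one in-range pressure qualify a subject however high the other is: 180/90 is eligible, 160/75 is not

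*Combined protocol and SAP*

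**What the plan says.** Criterion 2 of the Inclusion Criteria (Section 4.0) requires "Systolic blood pressures between 110 to 150 mmHg and/or diastolic blood pressure between 80-99 mmHg". This is the only blood pressure limit for entry. Among the 13 exclusion criteria, the one that bears on hypertension concerns drugs, not pressure: "Current use of anti-hypertensive medication (except calcium channel blockers and beta blockers".

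Section 2.0 describes the intended cohort as 200 people with pre-hypertension. Section 5.0 states the source: "Subjects will be recruited from the Outpatient Clinics at VUMC (including the General Medicine Clinic and the Hypertension Clinic", alongside emails, flyers and other tools.

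Section 6.0 randomises subjects once they are found eligible. One of the four arms is "oral administration of matching placebo", and treatment lasts 8 weeks. Blood pressure is measured at screening, but no limit is attached to that measurement.

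The other safeguards are general:
- Section 5.0: "All participants will have a baseline assessment, as well as on-going monitoring, of their health status as documented in their medical record".
- Section 6.0, Safety Precautions: "we will monitor blood pressure and electrolyte levels throughout the study".
- Section 6.0, Permanent stopping criteria: "There are any adverse events or clinical events that the PI judges increases the risk to the patient", and signs of declining health.
- Section 8.0: "Treatment will be discontinued for any subject who develops conditions during the course of the study", where those conditions are felt to alter the subject's risk/benefit balance significantly.

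**The concern.** The upper values of 150 and 99 mmHg look like caps, but joining the two windows with *and/or* removes their effect. Once one pressure lies in its window, the other may take any value. The wording was probably meant to admit someone whose other pressure falls below its window, such as 130/70 or 100/82. It does not say that, and it equally admits someone whose other pressure is far above its window.

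Two things are at stake. The first is safety. A subject with systolic pressure above 150 or diastolic above 99 could spend 8 weeks on placebo, having been barred at entry from antihypertensives other than calcium channel blockers and beta blockers. The second is fit to the target population, because such a subject does not belong in the pre-hypertensive cohort that the protocol describes. Recruitment from a hypertension clinic makes readings of this kind plausible at screening.

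**Working it through.** The plan gives no figure to reproduce here, so the check is a logical test of the criterion.

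**Inputs.** Systolic window 110–150 mmHg, diastolic window 80–99 mmHg, and the connector between them (Section 4.0, Inclusion Criteria). The readings below are chosen to illustrate the rule; they are not trial data.

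**Rules compared.**
- As written: eligible if 110 ≤ SBP ≤ 150 **or** 80 ≤ DBP ≤ 99.
- Strict *and*: eligible if both hold.
- Capped: as written, **and** SBP ≤ 150 **and** DBP ≤ 99.

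| Reading | As written | Strict *and* | Capped |
|---|---|---|---|
| 130/70 | yes | no | yes |
| 100/82 | yes | no | yes |
| 148/95 | yes | yes | yes |
| 180/90 | yes | no | no |
| 140/115 | yes | no | no |
| 160/75 | no | no | no |
| 160/105 | no | no | no |

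**Excess over the limits.**
- 180/90: 180 − 150 = 30 mmHg above the systolic limit, and eligible.
- 140/115: 115 − 99 = 16 mmHg above the diastolic limit, and eligible.
- 160/75: 160 − 150 = 10 mmHg above the systolic limit, and ineligible.

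**Ordering.** Compared with 160/75, the reading 180/90 is higher by 180 − 160 = 20 mmHg systolic and 90 − 75 = 15 mmHg diastolic. The rule admits the higher reading and refuses the lower. The same happens at the edge: 151/79 is ineligible and 151/80 is eligible, so one more mmHg of diastolic pressure brings in a subject whose systolic pressure is already over its limit.

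**Is there a ceiling elsewhere?** The 13 exclusion criteria set numeric limits for eGFR, BMI and transaminases, and none for blood pressure. The stopping criteria set one for potassium (above 5.5 mmol/L), and none for blood pressure. The blood pressure precaution in Section 6.0 is prompted by the risk that study drugs lower pressure too far. The discontinuation rule in Section 8.0 addresses conditions that arise during the study, whereas the pressure at issue is present at entry. The unblinded physician's stated role in Section 5.0 is limited to abnormal potassium. No other part of the document supplies the missing cap.

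**The case against.** The strongest reply is that the intent can be inferred. Read with the pre-hypertension label in Section 2.0, 150 and 99 are evidently upper limits and *and/or* is there for subjects whose other pressure is low, so this is loose drafting that a sensible investigator would not exploit. Meeting an inclusion criterion also does not compel enrolment. Screening includes a history and physical examination, vital signs are repeated at Week 0 before treatment starts and again at Weeks 2, 4 and 8, and the investigator may stop a subject for any event judged to raise risk. A placebo subject may be taking a calcium channel blocker or beta blocker. The drug exclusion removes many hypertension clinic patients. The example readings are extreme, and nothing in the primary analysis depends on the point.

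Much of this is fair, and it limits the size of the problem. The frequency is unknown, extreme cases may well be turned away, placebo exposure would not be unobserved, and the randomised comparison stays valid. It does not close the gap. The label in Section 2.0 is not an eligibility limit; if anything, it shows that the criterion admits people outside the intended cohort. The repeated measurements carry no numeric limit for high pressure. Staff who enrol a subject at 180/90 would be following the text, and two careful readers could classify that subject differently. An entry rule for a cohort defined by blood pressure should not depend on unwritten judgement.

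**Conclusion.** The concern holds. As worded, criterion 2 puts no upper limit on one pressure when the other is in range, and it can rank subjects in the wrong order. The conclusion rests on the ordinary inclusive meaning of *and/or* and on the absence of a cap anywhere else in the document.

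The criterion should be amended, but the defect is not fatal. The number of subjects who would enter above a limit cannot be estimated from the document. No sample size, power figure or primary analysis is affected. What is affected is the protection of subjects who may receive placebo and the match between the entry rule and the stated population.

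**What to change.** Reword criterion 2 to: systolic 110–150 mmHg and/or diastolic 80–99 mmHg, provided systolic is not above 150 mmHg and diastolic is not above 99 mmHg.

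This uses the protocol's own limits and excludes only subjects above one of them. Replacing *and/or* with a plain *and* would be the wrong repair, because it would also drop readings such as 130/70 and 100/82.

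The cost is a one-line eligibility amendment, possibly slightly slower recruitment, and a slightly narrower blood pressure range for Aim 1, which the existing windows already restrict. The change corrects entry only. It does not supply an in-study action level for a subject whose pressure rises after enrolment.

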##### Exclusion Criteria:

1. Pregnancy;
2. Intolerance to study protocols;
3. Acute cardiovascular events within the previous 6 months;
4. Impaired renal function (estimated GFR < 45 ml/min/1.73m^2);
5. Current or recent treatment with systemic glucocorticoid therapy (within 1 month of enrollment);
6. Current use of anti-hypertensive medication (except calcium channel blockers and beta blockers);
7. Diabetes mellitus requiring medical therapy;
8. Morbid obesity (BMI > 45);
9. Prior adverse reaction to a thiazide or spironolactone;
10. Claustrophobia preventing the patient from having an MRI or other contraindications to MRI;
11. Impaired hepatic function (aspartate amino transaminase and/or alanine amino transaminase > 1.5x upper limit of normal range);
12. Current illicit drug use.

13. Sexually active women of childbearing potential\*\* who are unwilling to practice adequate contraception during the study (adequate contraceptive measures include stable use of oral contraceptives or other prescription pharmaceutical contraceptives for 2 or more menstrual cycles prior to screening; intrauterine device [IUD]; bilateral tubal ligation; vasectomy; condom plus contraceptive sponge, foam, or jelly, or diaphragm plus contraceptive sponge, foam, or jelly).

\*\*Postmenopausal women must be amenorrheic for at least 12 months in order **not** to be considered of child bearing potential. Pregnancy testing and contraception are not required for women with documented hysterectomy or tubal ligation.

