#### Na+ storage and immune cell response

We have shown in animal experiments that Na+ storage in the skin and the resulting disequilibrium in interstitial Na+ concentration attracts macrophages, which then regulate clearance of electrolyte via cutaneous lymph capillaries, thereby controlling blood pressure by secretion of vascular endothelial growth factor C (VEGF-C). We also demonstrated that Na+ storage-driven

[figure not shown]
[figure not shown]

Fig. 6. Cross-sectional analysis of men with normal blood pressure (control), arterial hypertension (HTN), and men with HTN treated with the MR antagonist spironolactone (Spiro). Patients with the MR antagonist showed reduced Na+ storage in muscle. \* P(HTN) < 0.05; † P(Spiro) < 0.05. Adapted from Kopp et al., 2013.

immune responses can be pro-inflammatory and worsen auto-immune disease. We now aim for rapid transfer of these novel mechanistic insights on immune function into the clinical arena. Our general hypothesis is that age is associated with reduced beneficial homeostatic immune function, resulting in impaired tissue electrolyte clearance and accumulation of Na+ in the skin. Tissue Na+ accumulation in turn may promote separate pro-inflammatory immune-cell responses. The resulting vicious circle may lead to chronic inflammation and age-dependent development of cardiovascular disease. Our preliminary findings support this hypothesis. We found an inverse correlation between serum VEGF-C levels and skin Na+ content in our European subjects (Fig. 7), suggesting that age-dependent Na+ accumulation is due in part to reduced lymph capillary-driven tissue Na+ clearance. In our clinical prevention study proposed, we will test the hypothesis that increased Na+ storage is associated with a pro-inflammatory response and an anti-lymphangiogenic serum profile, which can be improved by therapeutic reduction of tissue Na+ content.

[figure not shown]

**Fig. 7.** Serum VEGF-C levels and skin Na+ content in humans. Skin Na+ accumulation is associated with low VEGF-C levels, suggesting impaired clearance of tissue Na+ via cutaneous lymph capillaries. Unpublished.

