missing link towards a new and better understanding of the chronic pro-inflammatory state that leads to cardiovascular disease with aging (Fig. 1). Similarly, Na+ stored in muscle may predispose to energy deficit and insulin resistance. Tissue Na+ storage thus may not only be pathophysiologically linked to arterial hypertension, but also with diabetes mellitus, another highly relevant cardiovascular risk factor. Successful therapeutic bending of the slope relationship between age and tissue Na+ accumulation (Fig. 1) therefore promises to become a novel, important approach for cardiovascular disease prevention.

In this clinical project, we will take the first step towards therapeutic “bending” of the age/Na+ accumulation relationship to a flatter slope (Fig. 2). We will establish a cohort of 200 subjects with pre-hypertension, age: 30 to 80 years. The cohort will be controlled for

gender, race, and age so that cross-sectional analysis of the cohort characteristics will provide us with new information on the effect of race on tissue Na+ content (Aim 1, Fig. 2). In a prospective, double-blinded randomized-controlled trial, we then will test the hypothesis that 8 weeks of a reduced salt diet or drug treatment with either the MR antagonist spironolactone, or with the diuretic hydrochlorothiazide, will reduce skin and muscle Na+ content (Aim 2, short-term longitudinal readout, Fig. 2). Tissue Na+ content will be our primary endpoint in Aims 1 and 2. As secondary endpoints, we will read out differences in blood pressure, skin forearm blood flow by BOLD MRI, and arterial stiffness by measurement of pulse wave velocity. Finally, we speculate that lower tissue Na+ content reduces a pro-inflammatory immune cell phenotype and improves insulin sensitivity (Aims 3 and 4). We will address the following specific aims:

- Specific Aim 1:** To test the hypothesis that African Americans are characterized by increased tissue Na+ storage, which is paralleled by higher blood pressure, reduced forearm blood flow, and enhanced pulse wave velocity
- Specific Aim 2:** To test the hypothesis that treatment with spironolactone reduces tissue Na+ content (Primary Outcome)
- Specific Aim 3:** To test the hypothesis that Na+ storage leads to immune cell activation (Secondary Outcome)

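### Exclusion 6 has no look-back for the drug classes the trial tests, so a just-stopped diuretic or MR antagonist can alter Week 0 values, mainly in the unadjusted Aim 1 race comparison

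*Combined protocol and SAP*

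**What the plan says.** Section 4.0, exclusion 6, bars "Current use of anti-hypertensive medication (except calcium channel blockers and beta blockers". The line above it, exclusion 5, is worded differently: "Current or recent treatment with systemic glucocorticoid therapy (within 1 month of enrollment". No washout, run-in or stable-dose rule for blood pressure drugs appears anywhere. Section 6.0 places screening within about two weeks of the start of treatment, as an outer limit and not as a minimum drug-free period.

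Section 5.0 says "Subjects will be recruited from the Outpatient Clinics at VUMC (including the General Medicine Clinic and the Hypertension Clinic". Section 2.0 describes the participants thus: "We will establish a cohort of 200 subjects with pre-hypertension, age: 30 to 80 years". The blood pressure entry rule, inclusion 2, is "Systolic blood pressures between 110 to 150 mmHg and/or diastolic blood pressure between 80-99 mmHg", and it does not say whether the reading is on or off treatment.

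Section 2.0 makes tissue Na+ the primary endpoint of Aims 1 and 2, with blood pressure and pulse wave velocity (PWV) secondary. Section 10.0 compares Week 0 blood pressure, forearm blood flow and PWV between races by two-sample t-test, with no covariates. Aims 3 and 4 correlate the change in Na+ with changes in immune activity and insulin sensitivity. Medication is reconciled at Week 0 (Section 6.0), but it is neither a stratification factor (Section 5.0) nor a named covariate (Section 10.0).

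**The concern.** The trial's premise is that the tested classes change tissue Na+, and Section 1.0 supports it with Fig. 6: "Patients with the MR antagonist showed reduced" muscle Na+ storage. On that premise, someone who stopped such a drug shortly before enrolment may start with a lowered Week 0 Na+ that moves during the eight weeks for reasons unrelated to the assigned arm. Week 0 blood pressure may be affected in the same way.

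What is at stake differs by aim:

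- **Aim 1** compares races without randomisation. If recent use differs by race, the difference passes directly into the estimate, and the planned t-test cannot separate it from a race effect.
- **Aims 3 and 4** use change in Na+, which can include drift from a previous drug. The regression in Section 10.0 names age, sex and body weight as examples of adjustment factors, not prior treatment.
- **Aim 2** is randomised, so prior use is balanced in expectation. Only extra variability is at issue.

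A separate matter is the exception for calcium channel and beta blockers. It lets a treated hypertensive qualify on a treated pressure, so Week 0 blood pressure and PWV in Aim 1 can mix on- and off-treatment values.

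**Working it through.** **1. Wording.** Exclusion 5 covers current or recent use with a one-month window. Exclusion 6 covers current use with no window. Both stand in the same list, and nothing elsewhere supplies the missing interval.

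**2. The plan's own figures.**

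- Aim 1: 100 per group, effect size 0.42, two-sided 5%. A t-test has 84.0% power, against the stated 85%.
- Aim 2: difference 5 mmol/L, SD 6.0, so effect size 5/6.0 = 0.833, with 85% power. A t-test needs 39.3, so 40 per group, at 1%, and 40.7, so 41 per group, at 0.05/6 = 0.0083 (six pairs of four arms). The stated 41 is reproduced with the latter, which rounds to 1%.

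**3. Aim 1, illustration.** Every input in this step except the 100 per race group is an assumption. Let the race groups differ by *d* in the share of affected subjects, and let being affected shift the outcome by *e* SD. Then

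- bias *b* = *d* × *e*;
- rejection rate under a true null = 1 − Φ(1.96 − *b*/√(2/100)) + Φ(−1.96 − *b*/√(2/100)), with √(2/100) = 0.141.

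| *d* | *e* (SD) | *b* (SD) | *b*/0.141 | Rejection rate |
|---|---|---|---|---|
| 0.05 | 0.25 | 0.0125 | 0.09 | 5.1% |
| 0.10 | 0.50 | 0.05 | 0.35 | 6.4% |
| 0.20 | 0.50 | 0.10 | 0.71 | 10.9% |
| 0.30 | 0.83 | 0.249 | 1.76 | 42% |

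The last row takes *e* equal to the full planned drug effect (5/6.0) and is an extreme. The bias may run in either direction, since the documents do not say which group would have more prior use.

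**4. Aim 2, illustration.** Assume that a share *p* of subjects, independent of arm, carries a drift of 5 mmol/L, equal to the plan's drug effect. Then SD = √(36 + *p*(1 − *p*) × 25). T-test power at 41 per group:

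| *p* | SD | Power at 1% | Power at 0.05/6 |
|---|---|---|---|
| 0 | 6.00 | 86.8% | 85.4% |
| 0.10 | 6.18 | 84.3% | 82.7% |
| 0.20 | 6.32 | 82.4% | 80.6% |
| 0.30 | 6.42 | 80.9% | 79.1% |

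If all 200 subjects are randomised, 50 per arm, power at *p* = 0.30 is 89.4% at 1% and 88.2% at 0.05/6.

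**5. Label.** The pre-hypertension description in Section 2.0 stands beside an entry range reaching 150 and/or 99 mmHg and an exception for two blood pressure drug classes. Both the range and the exception bear on the label, so a look-back in exclusion 6 would not by itself settle it.

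**The case against.** The strongest reply is that carry-over is not shown. Fig. 6 is cross-sectional, in men, in muscle, and in patients taking spironolactone. It says nothing about the period after stopping. The interval between screening and Week 0 may itself give some time off drug. This stands: the documents support saying that Week 0 values can be altered, not that they are.

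A reader might infer four stronger things, none of which the documents support:

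- **That exclusion 6 goes by indication, so a diuretic taken for oedema slips through.** Its exceptions are drug classes, and the safety paragraph of Section 6.0 groups the study drugs as anti-hypertensive/diuretic medication. Naming the classes is a matter of clarity only.
- **That the permitted blockers distort tissue Na+.** Nothing in the documents says these classes change it. The exception is explicit and looks deliberate. Its clear effect is on blood pressure and possibly PWV, both secondary endpoints. Even there, subjects are selected on measured pressure, so enrolled users need not read lower than enrolled non-users by the full effect of their drug.
- **That Aim 2 is biased.** Randomisation protects the contrast between arms. Section 10.0 does not say that 6.0 is an SD of change. If Week 8 content is compared and the earlier drug has worn off by then, even the power loss essentially disappears.
- **That the one month of exclusion 5 is the right interval here.** It concerns another class and is nowhere tied to tissue Na+. It shows that the authors use look-backs, not how long this one should be.

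The reply does not remove the gap in the text or the lack of adjustment in Aim 1.

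**Conclusion.** The point holds as a cheap improvement. As written, exclusion 6 admits subjects who have only just stopped a drug of the classes under test, and no other provision closes the gap. The consequence is possible, not demonstrated, because the share of such subjects and the duration of any effect are both unknown.

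Aim 1 carries the case. With a race difference of 10-20 points in prior use and a shift of 0.5 SD (both assumed), the nominal 5% error becomes about 6-11%. Smaller inputs leave it near 5%, and the most extreme combination shown gives 42%. In Aims 3 and 4, drift can enter the Na+ change; its effect on the correlations cannot be sized from the documents. In Aim 2 the cost is at most modest noise, about 3-6 points of power at 41 per group under the assumptions shown.

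The blocker exception is a separate and smaller matter, confined to how Week 0 blood pressure and PWV are read in Aim 1.

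**What to change.** 1. Reword exclusion 6 to cover current or recent use, with a look-back counted to the Week 0 MRI and its length set and justified by the sponsor. Name diuretics and MR antagonists explicitly.
2. Keep the calcium channel and beta blocker exception. Prespecify an Aim 1 sensitivity analysis of blood pressure and PWV by Week 0 blocker use: once adjusted for use, and once in subjects on neither class.
3. Reconcile the pre-hypertension label in Section 2.0 with inclusion 2 and exclusion 6, and state whether the qualifying pressure may be an on-treatment reading.

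The cost is one reworded criterion, a question about last use at screening, and one covariate from the medication reconciliation already collected. The downside is that some recently treated clinic patients become ineligible or enrol later.
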